## **5. Venipuncture:**

Laboratory analyses will include: CBC, CMP at procedure visit #1 only.

HIV antibody for participants that are not known to be HIV+ if no HIV testing available within the past 1 year.

Fasting IGF-I, IGF-BP3, total/free testosterone, IL-6, sTNFRI and sTNFRII, insulin and glucose will be evaluated at procedure visits #1 and #2, and at week 14, at least 48 hours following the last exercise session.

Inflammatory markers (IL-6, sTNFR-1, and TNF-alpha) will be measured pre-exercise, and 0, 60, or 90 minutes, and ~ 24 hours after a high-intensity exercise stimulus at week 2, 12, and 24.

For the optional microbiome substudy, EDTA plasma samples will be assessed for LPS, heparin plasma samples for sCD14, iFABP) and CRP. LPS levels will be measured using the Limulus Amebocyte Lysate (LAL) assay (Lonza, Switzerland) with plasma samples diluted 1:10 in endotoxin free water and heat-inactivated at 80°C for 15min. Commercially available ELISAs will be used to evaluate levels of IL-6, sCD14, and iFABP (all R&D Systems, Minneapolis, MN). Serum LBP levels were assessed using a custom ELISA all as reported in Dillon 2014.

Peripheral blood mononuclear cells (PBMCs) will be collected at each of the pre-exercise acute visits (weeks 2, 12, and 24) and stored. Future analyses (pending funding) will include an assessment of markers of T-cell and B-cell activation

Samples will be stored for additional analyses. These assays will be performed from stored specimens (in batch to minimize inter-assay variability) in the Clinical Translational Research Center (CTRC) core laboratory at UCD or by [name] in [name] laboratory. **All participant samples will be drawn between 7:30-10am. We will draw approximately 70 mL at the initial visit and 75 mL at the subsequent 3 visits.**

Risk: There is a small risk of local hematoma or infection associated with blood sampling.

Plans to minimize risk: The risks of hematoma and infection are minimized by having trained clinical personnel perform the procedures using sterile techniques.

Justification: We will be evaluating the response of HIV+ vs HIV- individuals to an exercise intervention, in hormone levels and markers of inflammation. Additional samples will be collected for storage. These safety and efficacy markers will be imperative in the design of future, larger intervention studies of exercise in HIV.

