**Analysis Plan:** Given repeated measurements over time, a linear mixed effects model will be used with change from week 0 as the primary outcome. The inclusion of additional time points will provide additional power. Groups defined by HIV-status (Exercise Intensity) will be evaluated. The baseline value and a group and time interaction term will be included as model predictors. The primary analysis will be intent to treat. Baseline (week 0) characteristics will be compared between groups prior to comparisons of endpoints, with log transformation for normality, as appropriate. The primary analysis will consider adjusting for age, smoking, exercise intensity (HIV-status) and body mass index (BMI); although if matching and/or balance by group is achieved, they may be precision variables, but they cannot be confounders. Finally, given the potential for non-ignorable dropout, we will accommodate dropout in the analysis of functional measures using a semi-parametric varying-coefficient model approach [150]. The primary analyses will assume that the slope beyond dropout is linear with sensitivity analyses utilizing a slope is attenuated by 50% and a zero slope beyond dropout, the latter being similar to a last value carried forward. Additionally a sensitivity analysis using only data from study completers will be conducted.

Change in IGF-I mRNA will be a primary outcome in the subset of participants undergoing muscle biopsy.

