Outcome measures will be available bi-weekly for chair rise, and three times for other functional measures. Serum IGF-I, IGFBP3, muscle IGF-1 mRNA/protein, visceral fat, LBM, and inflammatory cytokines will be measured at procedure visits #1 and #2. Secondary outcomes will include change in other cytokines and hormones, sleep quality, quality of life, V02 peak, strength, and modified SPPB. The inflammatory markers will be tested as mediators on the effect of exercise on changes in function and LBM. Additional secondary outcomes will determine if sedentary time increases as the physical activity intensity decreases, the impact of the intervention on the affect and efficacy of exercise. These factors will be important in design of larger interventions and dissemination to identify points of low exercise efficacy and poor affect and attempt to prevent drop-outs from the intervention. An important outcome is to ensure that intensive 3x/week physical activity does not lead to a decrease in usual activity and an increase in sedentary time due to exercise-related fatigue.

For the inflammatory analyses:

**Analysis.** We propose that no subjects in either arm will experience a major injury (e.g., muscle strain or other injury requiring self-prescribed or provider prescribed treatment) and no more than 1 subject in each group will drop out because of exercise-induced discomfort

(i.e., fatigue, muscle or joint pain). The step counts between arms will be compared to determine if the high-intensity group limits non-study activity. For Aim 3, we will compare the change between arms in IL-6, TNF $\alpha$  and sTNFRI (pre-exercise, and 0, 60, and 90 minutes, and 24 hours) with a single bout of exercise at weeks 2, 12, and 24. We also will compare relative changes in serum IL-6, TNF $\alpha$  and sTNFRI from week 2 to week 24 between groups using geometric means and 95% confidence intervals. Secondary outcomes will include the change in other inflammation (sTNFRII, hsCRP, IL-10) and immune activation (sCD14, sCD163) markers, change in physical function, QoL, depressive symptoms, and exercise self-efficacy between study arms. **Sample size and power.** Sample size calculations were conducted for the within and between group percent change in IL-6, TNF $\alpha$ , hs-CRP, and sTNFRI levels. Data from 49 HIV+ subjects with higher function were used to estimate sample size parameters. We anticipate additional power using

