Table 3. Detectable % change from geometric mean needed to achieve 80% power

Outcome	Geometric Mean	Mean (SD) log scale	Within Group Change*		Between Groups Change	
			Increase	Decrease	Increase	Decrease
IL-6 (pg/mL)	0.98	-0.025 (0.629)	52%	34%	110%	52%
TNF $\alpha$ (pg/mL)	1.48	0.392 (0.274)	20%	17%	37%	28%
hs-CRP (mg/L)	1.55	0.440 (1.21)	120%	55%	300%	75%
sTNFRI (pg/mL)	997.9	6.91 (0.25)	24%	19%	34%	25%

\*standard deviation (SD) adjusted based on a 0.7 correlation between paired measurements.

the summary measure AUC. Table 3 contains the within and between group detectable percent change from the geometric mean was calculated assuming a sample size of 13 subjects per group, 80% power, a significance level of 0.05 and a two-sided two-sample t-test.

For the qualitative interviews:

Data Analysis: We will analyze transcribed interviews using a mixed inductive and deductive approach. To develop the codebook, a qualitative analyst and the PI will code a subset of interviews separately using ATLAS.ti software. Coding differences will be adjudicated by [name] (Co-I). The analyst will then code the remainder of the interviews. After open coding, key meanings and insights will be identified and then reduced to identify patterns. Themes will be explored and tested using iterative techniques across subsequent individual and group level interviews.

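### The resting-inflammation comparison of exercise intensities is a week-24 to week-2 ratio with no baseline covariate, although two pre-randomisation marker values are available to sharpen it

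*Combined protocol and SAP*

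**What the plan says.** Under Specific Aim 3, the hypothesis on 24 weeks of training concerns resting IL-6, sTNFRI and TNF-alpha. It expects a greater relative decline in HIV+ adults on high intensity than in those on moderate intensity or in HIV- adults.

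The inflammatory analyses in IV.F have their own method for this: relative changes are compared "from week 2 to week 24 between groups using geometric means and 95% confidence intervals". No model, covariate or missing-data rule is given there. Table 3 was calculated "assuming a sample size of 13 subjects per group, 80% power, a significance level of 0.05 and a two-sided two-sample t-test". Its footnote, on the within-group columns, says that the SD was "adjusted based on a 0.7 correlation between paired measurements".

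The Analysis Plan paragraph of IV.F does describe a linear mixed model with the baseline value as a predictor, but for change from week 0 as the primary outcome. Its dropout provision is limited: "we will accommodate dropout in the analysis of functional measures".

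On sampling, IV.D.5 (Venipuncture) states: "Inflammatory markers (IL-6, sTNFR-1, and TNF-alpha) will be measured pre-exercise", with post-exercise draws up to about "24 hours after a high-intensity exercise stimulus at week 2, 12, and 24". A separate fasting set, which includes IL-6 and sTNFRI but does not list TNF-alpha, "will be evaluated at procedure visits #1 and #2, and at week 14". Under IV.C, randomisation takes place at week 13 among participants still on study. The week-2 and week-12 pre-exercise samples are therefore both pre-randomisation values.

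**The concern.** A log ratio of week 24 to week 2 fixes the slope on the starting value at 1. With two measurements correlated at less than 1, that slope is too steep and adds noise that a covariate adjustment would remove. The week-12 value, the last before randomisation and the closest to the outcome, is used in the acute-bout comparison but not in the resting contrast.

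A ratio also needs both samples. A randomised participant without a week-24 sample drops out of the comparison, and no dropout method is stated for these markers.

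What is at stake is mainly precision. The intensity contrast within HIV+ participants starts from 18 per arm, and Table 3 shows that only large differences in IL-6 are detectable at this size.

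**Working it through.** **Inputs.** IL-6 log-scale SD 0.629 and paired correlation r = 0.7 (Table 3 and its footnote); 13 per group, 80% power, two-sided 0.05 (text below Table 3); 18 per arm within each HIV stratum (randomisation table in IV.F). An illustrative 14 per arm is 18 × 0.8 = 14.4. It borrows the chair-rise dropout allowance of about 20% at week 16; the plan gives no loss rate after randomisation.

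**1. Reproduce the plan's figure.** For a two-sample t-test (noncentral t, 24 df) with 13 per group, the detectable log difference is 1.145 × SD.
- With the single-time SD: 1.145 × 0.629 = 0.720, so exp(0.720) − 1 = 105.5% increase and 1 − exp(−0.720) = 51.3% decrease.
- Table 3 states 110% and 52%. Power at the stated 52% decrease is 81.4%.

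The between-group columns therefore rest on the SD of one measurement, not on the SD of a change.

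**2. Variance of the planned ratio and of the adjusted analysis**, in units of the single-time variance:
- log ratio: 2(1 − r) = 2(0.3) = 0.60
- adjusted for week 2: 1 − r² = 1 − 0.49 = 0.51
- 0.51/0.60 = 0.85, which is 15% lower
- adjusted for weeks 2 and 12, all correlations 0.7 (assumption): 1 − 2r²/(1 + r) = 1 − 0.98/1.7 = 0.424, and 0.424/0.60 = 0.71

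**3. Detectable IL-6 difference** (increase / decrease):

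| Analysis | 13 per group | 14 per arm |
|---|---|---|
| Log ratio, SD 0.629 × √0.60 | 74.7% / 42.8% | 70.9% / 41.5% |
| Adjusted for week 2, SD 0.629 × √0.51 | 67.3% / 40.2% | 63.9% / 39.0% |
| Adjusted for weeks 2 and 12, SD 0.629 × √0.424 | 59.8% / 37.4% | 56.9% / 36.3% |

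The multiplier at 14 per arm is 1.100.

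**4. Sensitivity to r.** The ratio (1 − r²)/[2(1 − r)] simplifies to (1 + r)/2. It is 0.65 at r = 0.3, 0.75 at 0.5, 0.85 at 0.7 and 0.95 at 0.9.

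**5. Cost of estimating slopes.** Steps 2 and 3 treat the slopes as known. With p covariates and n per arm, the expected variance inflation is about 1 + p/(2n − p − 3). At n = 13 this is 1 + 1/22 = 1.045 for one covariate and 1 + 2/21 = 1.095 for two. The net variance ratios are about 0.85 × 1.045 = 0.89 and 0.71 × 1.095 = 0.77. The gain shrinks but remains.

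**6. Retaining participants without a week-24 sample.** Assume 18 per arm, 10 to 20% missing at week 24, and a week 12 to 24 correlation of 0.7 to 0.8. A repeated-measures likelihood model then has about 2 to 7% less variance than the week-2-adjusted analysis of participants with week-24 data. That calculation lets week 12 act as an intermediate measurement. Once week 12 is a covariate, someone with no later sample adds little to the arm contrast, so a few percent is an upper guide.

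**The case against.** **The plan may already cover this.** The general Analysis Plan has a mixed model, the baseline value as predictor, intent to treat and log transformation. Geometric means with CIs could be only a reporting scale. This deserves weight, because no complete-case rule is written. But that model is for change from week 0, the inflammatory section starts at week 2 and has its own paragraph, and its sizing uses a t-test without covariates. An unadjusted ratio is the fair reading. If the sponsor meant otherwise, one sentence settles it.

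**The ratio is valid.** Under randomisation and complete data it is unbiased, so adjustment is a precision choice, and the gain is modest. That stands.

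**Stronger readings that the documents do not support.**
- A reader might apply the roughly 20% dropout and say that about 7 of 36 per group are excluded. That allowance is for week 16 in the chair-rise sizing. Only those still on study at week 13 are randomised, so earlier losses never enter the intensity contrast, and the number lost later is not given.
- A reader might say that most dropouts have a week-12 value. By schedule this holds for people lost after randomisation. For all enrolled it is not shown, because the timing of dropout is not stated.
- A reader might say that week-12 data would correct a ratio that flatters high intensity, since the Background warns that hard exercise may raise inflammation in some people. Everyone trains at moderate intensity until week 13, so week 12 carries no information on response to high intensity. The direction of any such bias is a possibility, not something that the documents establish.

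**Conclusion.** For the randomised intensity contrast, the planned ratio gives up precision that pre-randomisation samples could supply. At r = 0.7 the variance is 15% lower with week 2 as a covariate (about 11% lower after the cost of estimating the slope at 13 per group). With week 12 added it is about 0.71 of the change-score variance (about 0.77 after that cost) if all correlations are 0.7. The gain depends on r and is small near r = 0.9.

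Table 3's stated detectable changes are not overstated. Its between-group IL-6 decrease of 52% is more conservative than the 42.8% that the planned ratio would give at r = 0.7, so there is no power shortfall here.

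The missing-data side is secondary. A likelihood model handles only dropout that is explained by observed values. It does not remove bias from people leaving because of their response to high intensity.

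The point is confined to the randomised contrast. HIV+ and HIV- groups are not randomised, and the efficiency argument above does not carry over to them.

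**What to change.** In the inflammatory analyses of IV.F, state for the randomised intensity contrast:

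1. The outcome is the log week-24 pre-exercise value of each marker, with the log week-2 and week-12 pre-exercise values as covariates. Report adjusted geometric mean ratios with 95% CIs.
2. The missing-data rule. A log-scale likelihood-based repeated-measures model may be used to retain randomised participants without a week-24 sample. Week 12 must then enter as a pre-randomisation value, not as a post-randomisation outcome.
3. Fasting samples (procedure visits and week 14) are kept distinct from the acute-visit pre-exercise samples, before which a snack is allowed, and are not pooled as one series. Week 14 does not list TNF-alpha.
4. The week-24 to week-2 ratio in participants with both samples is a sensitivity analysis.
5. The number randomised and the number without a week-24 sample are reported by arm.

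The cost is SAP wording and modest programming. No extra samples or visits are needed.

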## **F. Data Analysis Plan:**

### **Statistical Considerations**

Sample Size Calculations: The primary outcome for sample size calculations is change from baseline in chair rise pace. We assume a change from baseline of 1.5 (SD=1.54) seconds or larger, based on differences observed by fall history [85]: Sample sizes of 36/group will yield an estimate of 29 patients per group at week 16 (~20% dropout). 29 subjects per group achieves over 80% power to detect a between group difference of 1.5 seconds with a significance level of 0.05 and the standard deviation conservatively estimated at 2.0 seconds[110] using a two-sided two-sample equal variance t-test.

Matching and Randomization: Enrollment in the uninfected arm will be constrained to lag behind HIV-enrollments. Upon the enrollment of every 5th HIV-infected patient, HIV-uninfected enrollment will be evaluated and recruiting goals updated to ensure a similar age (<60; >=60), gender, BMI, and smoking

distribution. Given the smaller proportion of women in the HIV-infected population, we plan to enroll fewer women. The randomization will be blocked by gender and exercise intensity to ensure balance according to the following scheme:

Exercise Intensity	Moderate (N=36)		High (N=36)	
HIV-Infected (N=36)	Men:	15	Men:	15
	Women:	3	Women:	3
Controls (N=36)	Men:	15	Men:	15
	Women:	3	Women:	3

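### Table 3 (Aim 3 power): the sTNFRI within-group entry of 24%/19% should be 18%/15% on the method of the other rows, and the between-group columns use a single-measurement SD although changes will be compared

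*Combined protocol and SAP*

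**What the plan says.** The material is in section IV.F (Data Analysis Plan), in the inflammatory analyses part of Statistical Considerations.

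- **Planned comparisons.** For the acute response, "For Aim 3, we will compare the change between arms in IL-6" and the other markers around a single exercise bout. For the chronic response, relative changes in the markers are compared "from week 2 to week 24 between groups using geometric means and 95% confidence intervals".
- **Source of the SDs.** "Data from 49 HIV+ subjects with higher function were used to estimate sample size parameters".
- **Method sentence.** The detectable changes were calculated "assuming a sample size of 13 subjects per group, 80% power, a significance level of 0.05 and a two-sided two-sample t-test". No other test is named.
- **Table 3 footnote**, marked only on the within-group heading: "standard deviation (SD) adjusted based on a 0.7 correlation between paired measurements".

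Table 3 entries (detectable increase / decrease):

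| Marker | SD, log scale | Within group | Between groups |
|---|---|---|---|
| IL-6 | 0.629 | 52% / 34% | 110% / 52% |
| TNF-alpha | 0.274 | 20% / 17% | 37% / 28% |
| hs-CRP | 1.21 | 120% / 55% | 300% / 75% |
| sTNFRI | 0.25 | 24% / 19% | 34% / 25% |

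**The concern.** The sTNFRI row looks wrong on its face. sTNFRI has the smallest log-scale SD in the table, yet its within-group detectable change is larger than that of TNF-alpha, whose SD is larger. With sample size, power, level and correlation held fixed, that ordering cannot arise.

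There are two further problems. A two-sample test cannot be the test behind a within-group change. And the between-group columns carry no correlation adjustment, although the quantity to be compared between groups is a change, whose SD depends on that correlation.

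Aim 3 includes the randomised comparison of high with moderate intensity. A reader judging what that comparison can detect cannot rebuild the table from the method given, and cannot tell which correlation the between-group figures assume.

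**Working it through.** **Inputs.** n = 13 per group, 80% power, two-sided 0.05, correlation r = 0.7 and the four log-scale SDs, all from Table 3 and its text.

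**Formulas.** On the log scale the detectable difference is D = d × SD, reported as exp(D) − 1 for an increase and 1 − exp(−D) for a decrease. From the exact noncentral t distribution with n = 13:

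- paired t-test: d = 0.8467
- two-sample t-test: d = 1.1454

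The SD of a change is SD × √(2(1 − r)). At r = 0.7 this is 0.7746 × SD; at r = 0.5 it equals SD.

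**Step 1: reproduce the within-group columns.** With a paired test at r = 0.7, D = 0.8467 × 0.7746 × SD = 0.656 × SD.

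| Marker | D | Computed | Printed | Printed log change ÷ SD |
|---|---|---|---|---|
| IL-6 | 0.4125 | 51.1 / 33.8 | 52 / 34 | 0.666 / 0.661 |
| TNF-alpha | 0.1797 | 19.7 / 16.4 | 20 / 17 | 0.665 / 0.680 |
| hs-CRP | 0.7935 | 121.1 / 54.8 | 120 / 55 | 0.652 / 0.660 |
| sTNFRI | 0.1640 | 17.8 / 15.1 | 24 / 19 | 0.860 / 0.843 |

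Any single method gives one ratio in the last column for every row. Three rows agree with 0.656 to within rounding or a little more; sTNFRI does not.

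Rounding of the printed SD does not explain it: 0.245 to 0.255 gives only 17.4–18.2 / 14.8–15.4. A misprinted SD is also unlikely, because the between-group entry in the same row fits 0.25 (step 3). At r = 0.7, a 24% increase has 95.6% power and a 19% decrease 94.9%.

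The documents do not show the cause. At least two slips would give the printed values: a paired test with the unadjusted SD (23.6 / 19.1), or a two-sample normal approximation with the adjusted SD (23.7 / 19.2).

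**Step 2: take the method sentence literally.** A two-sample t-test with the adjusted SD gives D = 1.1454 × 0.7746 × SD = 0.887 × SD. The within-group columns would then be IL-6 74.7 / 42.8, TNF-alpha 27.5 / 21.6, hs-CRP 192.6 / 65.8 and sTNFRI 24.8 / 19.9. The first three are far from the printed values.

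**Step 3: reproduce the between-group columns.** A two-sample t-test with D = 1.1454 × SD, the SD of one measurement, is compared with the same test on the SD of change at r = 0.7:

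| Marker | Printed | Single-measurement SD | SD of change, r = 0.7 |
|---|---|---|---|
| IL-6 | 110 / 52 | 105.5 / 51.3 | 74.7 / 42.8 |
| TNF-alpha | 37 / 28 | 36.9 / 26.9 | 27.5 / 21.6 |
| hs-CRP | 300 / 75 | 299.8 / 75.0 | 192.6 / 65.8 |
| sTNFRI | 34 / 25 | 33.2 / 24.9 | 24.8 / 19.9 |

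The printed columns follow the single-measurement SD. The loosest fits are the IL-6 increase (110 against 105.5) and the TNF-alpha decrease (28 against 26.9).

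**Step 4: what the printed between-group increases mean for a contrast of changes.** Power across the four markers, 13 per group, by correlation:

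| r | Power |
|---|---|
| 0.7 | 95–96% |
| 0.5 | 80–82% |
| 0.3 | 66–68% |
| 0 | 51–53% |

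**The case against.** **The replacement value is not established.** If the cause is unknown, 18%/15% is chosen by majority of rows. The literal method sentence gives sTNFRI 24.8/19.9, within about a point of the printed 24/19, so this may be the one row that follows the text. This does not hold up. A within-group change calls for a paired (one-sample) test whatever the author did. The literal reading rounds to 25/20, and it breaks the other three rows.

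**The test name is a wording slip.** The footnote speaks of paired measurements, so a careful reader can infer a paired test. That is fair, and it recovers three rows. It does not recover the fourth, and the sentence still names the wrong test for half the table.

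**The raw SD is a common conservative choice.** The footnote is marked only on the within-group heading, and the plan never states r = 0.5; that is a translation of the raw SD into a contrast of changes. This stands in part: the footnote is not breached, and the choice can be defended. But the plan does compare changes, so the translation is needed to read the columns, and the choice should be declared. A correlation below 0.5 is hypothetical, though the documents give no support for 0.7 either.

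**No decision turns on it.** This largely stands. Enrolment was set on a different endpoint: "The primary outcome for sample size calculations is change from baseline in chair rise pace". The 13 per group in Table 3 is also below the 18 HIV-infected participants planned per intensity arm. That limits the weight of the point but does not make the printed figures right.

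**Conclusion.** The concern holds. The sTNFRI within-group entry is wrong on the method of its own column: 18%/15%, not 24%/19%. The named test does not produce the within-group columns. The between-group columns match a contrast of changes only at r = 0.5, while the adjacent columns assume 0.7; at 0.7 the detectable changes would be IL-6 75%/43%, TNF-alpha 28%/22%, hs-CRP 193%/66% and sTNFRI 25%/20%.

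These figures take the printed SDs, n = 13 and r = 0.7 as given. On those terms both discrepancies overstate the detectable change, so no sample size is shown to be too small. That reassurance depends on the correlation: if it were below 0.5, the between-group columns would understate the detectable change. The primary chair-rise calculation is not touched. This is a correction that should be made to the stated power for Aim 3, not a flaw in the design.

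**What to change.** 1. Change the sTNFRI within-group cells to 18% and 15%.
2. Reword the method sentence: a paired t-test on the log scale for the within-group columns, and a two-sample t-test on log change for the between-group columns.
3. Either recompute the eight between-group cells with the SD of log change at r = 0.7 (the values in the verdict), or keep them and add a footnote saying that they use the single-measurement SD, equivalent to r = 0.5 for a change, as a deliberately conservative choice.

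The cost is two cells, one sentence, and either eight cells or one footnote. Nothing in the design, enrolment or data collection changes.

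### Table 3's between-group columns use the single-time SD, so under the plan's own 0.7 correlation they understate Aim 3's sensitivity to differences in change (IL-6: printed 110%/52%, about 75%/43% on the SD of change)

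*Combined protocol and SAP*

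**What the plan says.** Section IV.F, under the inflammatory analyses, plans two kinds of Aim 3 comparison. The first compares arms on the change in IL-6, TNF-alpha and sTNFRI with a single exercise bout at weeks 2, 12 and 24. The second compares relative changes in the same markers "from week 2 to week 24 between groups using geometric means and 95% confidence intervals". The power paragraph then states: "Sample size calculations were conducted for the within and between group percent change in IL-6", TNF-alpha, hs-CRP and sTNFRI. The inputs are log-scale SDs from 49 HIV+ subjects with higher function.

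Table 3 is titled "Detectable % change from geometric mean needed to achieve 80% power". It gives one log-scale SD per marker, two within-group columns and two columns headed as between-groups change. The stated conditions are "assuming a sample size of 13 subjects per group, 80% power, a significance level of 0.05 and a two-sided two-sample t-test". An asterisk on the within-group heading leads to the footnote: "standard deviation (SD) adjusted based on a 0.7 correlation between paired measurements". The between-group heading has no asterisk, and the text does not say why. It adds only that more power is expected from the AUC summary measure.

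**The concern.** The SD that governs a between-group comparison of change is the SD of change, not the SD of a level at one time. If each marker has the same SD at both times and correlation rho between them, the SD of the log change is SD x sqrt(2(1-rho)). At rho = 0.7 that is 0.775 x SD. Table 3 makes this adjustment for change within a group and omits it for the difference in change between groups, so it uses two variances for the same quantity.

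At stake is the stated sensitivity of Aim 3. Someone using Table 3 to judge what a null result could have missed would conclude that only very large effects, such as a doubling of IL-6, were within reach.

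**Working it through.** **Inputs (Section IV.F and Table 3).** n = 13 per group, 80% power, two-sided 0.05, two-sample t-test; log SDs of 0.629 (IL-6), 0.274 (TNF-alpha), 1.21 (hs-CRP) and 0.25 (sTNFRI); rho = 0.7 from the footnote.

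**Formula.** On the log scale the detectable difference is D = d x SD, where d solves the noncentral-t power equation. The detectable increase is exp(D) - 1 and the decrease is 1 - exp(-D). For two groups of 13, d = 1.145. For a paired test in one group of 13, d = 0.847.

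**Step 1: reproduce the printed between-group columns, then use the SD of change.** For IL-6 on the raw SD, D = 1.145 x 0.629 = 0.720, giving +105.5%/-51.3%. The SD of change is 0.629 x sqrt(0.6) = 0.487, so D = 1.145 x 0.487 = 0.558, giving +74.7%/-42.8%. All markers (increase/decrease, %):

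| Marker | Printed | Raw SD | SD of change, rho 0.7 |
|---|---|---|---|
| IL-6 | 110/52 | 105.5/51.3 | 74.7/42.8 |
| TNF-alpha | 37/28 | 36.9/26.9 | 27.5/21.6 |
| hs-CRP | 300/75 | 299.8/75.0 | 192.6/65.8 |
| sTNFRI | 34/25 | 33.2/24.9 | 24.8/19.9 |

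The raw SD matches every entry to about one percentage point except the IL-6 increase. There, 105.5 would print as 110 if values above 100% were rounded to the nearest ten, as the other such entries appear to be. The SD of change matches none. With the SD of change, power at the printed IL-6 increase of 110% is about 96%.

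**Step 2: check the within-group columns.** Using d = 0.847 and the 0.7-adjusted SD:

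| Marker | Printed | Adjusted SD | Unadjusted SD |
|---|---|---|---|
| IL-6 | 52/34 | 51.1/33.8 | 70.3/41.3 |
| TNF-alpha | 20/17 | 19.7/16.4 | 26.1/20.7 |
| hs-CRP | 120/55 | 121.1/54.8 | 178.6/64.1 |
| sTNFRI | 24/19 | 17.8/15.1 | 23.6/19.1 |

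Three rows follow the footnote. The sTNFRI row follows the unadjusted SD and so contradicts it.

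**Step 3: dependence on the correlation.** IL-6, 13 per group, between-group difference in change:

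| rho | Increase/decrease (%) |
|---|---|
| 0.3 | 134.5/57.4 |
| 0.5 | 105.5/51.3 |
| 0.6 | 90.5/47.5 |
| 0.7 | 74.7/42.8 |
| 0.8 | 57.7/36.6 |

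At rho = 0.5 the SD of change equals the raw SD. The printed columns are too large only when rho exceeds 0.5.

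**Step 4: group sizes.** The design table in Section IV.F has 18 per HIV-by-intensity cell and 36 per HIV group or per pooled intensity arm. With the 20% dropout stated there for week 16, 18 x 0.8 = 14.4 (about 14) and 36 x 0.8 = 28.8 (about 29). On the SD of change at rho = 0.7, IL-6 is:
- 14 v 14 (d = 1.100): +70.9%/-41.5%
- 29 v 29 (d = 0.749): +44.0%/-30.6%

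**The case against.** The strongest defence is that this is a disclosed, conservative choice. The footnote openly limits the correlation to the within-group columns, and the cells follow from the SDs printed beside them. The trial's size comes from chair rise, not from Table 3. The marker analysis will report 95% confidence intervals, which show the precision achieved whatever the planning table says. All of this stands and limits the consequence. It does not make the columns right: the text says they give detectable between-group change, and a single-time SD does not give that under the table's own correlation. The extra power expected from AUC is not quantified and does not bear on the week 2 to week 24 comparison.

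A reader might infer more than the documents support on four points:

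- **That 13 per group fits no planned contrast.** Thirteen is one below the roughly 14 per intensity arm left within HIV+ after 20% loss, and that 20% is stated for week 16 while the endpoint is week 24. The gap moves IL-6 only from about 75% to 71%. The fair criticism is that the table does not name its contrast.
- **That the marker comparison is unadjusted for baseline.** The general Analysis Plan includes the baseline value as a model predictor. The marker paragraph does not say whether this carries over.
- **That Aim 3 is underpowered because of this.** At rho = 0.7 the error runs the other way.
- **That the printed IL-6 increase of 110% against 105.5% is a further slip.** Rounding probably explains it.

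**Conclusion.** The concern holds in a limited form. The between-group columns of Table 3 rest on the single-time SD although they are presented as detectable change. Under the table's own 0.7 they overstate the smallest detectable difference for all four markers, for IL-6 by about 35 percentage points on the increase (110 - 75). The within-group sTNFRI entry is separately inconsistent with the footnote.

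The corrected figures assume equal SDs at both times and in both groups, 13 per group, and rho = 0.7 applied to the between-group contrast. The plan gives 0.7 only for the within-group columns and no separate value for the acute-bout contrast, so the range in Step 3 should accompany any single figure. The direction reverses below 0.5. No enrolment number or primary conclusion changes. What changes is how a null Aim 3 result should be read.

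**What to change.** 1. Recompute the between-group columns with SD x sqrt(2(1-rho)). State rho, show a range (for example 0.5 to 0.8), and say which value is assumed for the acute-bout contrast and which for week 2 to week 24.
2. Name the contrast and group size behind each column: about 14 v 14 for intensity within HIV+ (IL-6 about +71%/-41%) and about 29 v 29 for HIV+ v HIV- or pooled intensity arms (IL-6 about +44%/-31%). Note that both use the dropout stated for week 16.
3. Correct the within-group sTNFRI entry to the footnote's adjustment (17.8/15.1), or explain why it differs.
4. Optionally, state that the general model's baseline adjustment extends to the log-scale marker comparisons. For the randomised intensity contrast the natural covariate is the week 12 pre-exercise value, the latest before randomisation at week 13. If rho between that value and the outcome were also 0.7, the residual SD would be SD x sqrt(1 - 0.49) = 0.714 x SD, and IL-6 at 13 per group would be about +67%/-40%.

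The cost is one recalculated table and a sentence or two in Section IV.F, with no extra participants, visits or samples.
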